3.14	Lens Removal	
Have the subject remove the study lenses and store in saline in a labeled glass vial.
 
NOTE: Lenses do not need to be stored in a refrigerator.
	
3.15	Biomicroscopy	
Perform Biomicroscopy OD and OS. Slit Lamp Classification Scales will be used to grade the findings.
 
For the conjunctival redness [REDACTED] 0.5 unit increments will be used in the grading.
 
Corneal Staining Assessment [REDACTED] will be graded in 1.0 increments.
 
If any of these slit lamp findings are Grade 3 or higher, an AE must be recorded. All AEs must be followed to resolution.
 
If the clearance of the fluorescein needs to be expedited, preservative-free rewetting drops may be instilled.
	[REDACTED]
3.16	Distance and Near Exit Visual Acuity	
Distance and near Snellen visual acuity will be measured for each eye with the subject's habitual correction in place.
 
For near measures use the ETDRS 2000 Series Chart 1 or 2.
 
The acuity will be recorded to the nearest letter OD, OS and OU.
	[REDACTED]
3.17	Schedule Follow-up	
The subject will complete a wash-out period and be scheduled to return for their next visit in 7 ± 3 days.
 
NOTE: Subject may wear their habitual spectacles or contact lenses during the washout period.
	

VISIT 4

The subjects may present to Visit 4 wearing their habitual spectacles or contact lenses, if required for their distance vision.

Visit 4: Baseline Treatment 2		
Step	Procedure	Details
4.1	Adverse Events and Concomitant Medications Review	Review the subject's concomitant medications and record any changes from the previous study visit.

Clinical Study Protocol
Johnson & Johnson Vision Care, Inc.

		Record any adverse events or medical history changes from the previous study visit.	
4.2	Subject Reported Ocular Symptoms	Subjects will respond to a verbal open-ended symptoms questionnaire.	[REDACTED]
4.3	Distance and Near Entrance Visual Acuity	
Distance and near Snellen visual acuity will be measured for each eye with the subject's habitual correction in place.
 
For near measures use the ETDRS 2000 Series Chart 1 or 2.
 
The acuity will be recorded to the nearest letter OD, OS and OU.
	[REDACTED]
4.4	Lens Removal (if applicable)	Have the subject remove their habitual lenses and store in an approved storage solution.	

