4.13	Distance Over-Refraction and Distance Visual Acuity	Perform a distance over-refraction OD and OS using loose lenses outside of the phoropter under ambient room illumination. The distance over-refraction may also be refined under binocular conditions. Record the results. The results of the distance over-refraction may also be checked for the impact on near vision under monocular and/or binocular conditions.	
4.14	Lens Fit Assessment	
Evaluate overall lens fit acceptance (acceptable or unacceptable) based on centration, movement and other fitting characteristics.
 
An unacceptable fit is deemed by one of the following criteria:
 
 • limbal exposure at primary gaze or with extreme eye movement; • edge lift; • excessive movement in primary and up gaze; or 	

Clinical Study Protocol
Johnson & Johnson Vision Care, Inc.

		
 insufficient movement in all three of the following conditions: primary gaze, up gaze, and Josephson push up. 
If either lens is deemed unacceptable, the subject will be discontinued from the study. Remove the lenses, perform a slit-lamp evaluation, and complete the Final Evaluation form.
	
4.15	Modifications	
If the subject reports unsatisfactory vision, or is unable to obtain 20/30 distance visual acuity OU with the lenses then a modification must be attempted.
 
If the subject reports satisfactory vision with the lenses a modification is not required, however at the Investigator's discretion and based upon their findings on the measured visual acuity and/or over- refraction the investigator may make a modification.
 
Up to two attempts at modification are permitted if necessary, in order to achieve an acceptable distance and near binocular performance for the subject, and to enable them to wear that particular lens type. Follow the fitting guide allowing for at least 10 minutes of settling time between each lens modification attempted.
 
If modifications are required steps 4.8-4.14 will be repeated for each modification
	Appendix G (Fitting Guide)
4.16	Post-Fit PRO (MRD) Questionnaire	The subject will evaluate the vision characteristics, comfort characteristics, handling characteristics, and visual symptoms of the study lenses using the PRO questionnaire.	

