6.4	PRO (CLUE and MRD) Questionnaires and CLDEQ-8	The subject will evaluate the vision characteristics, comfort characteristics, handling characteristics, and visual symptoms of the study lenses using the PRO questionnaire.
6.5	Ocular Symptoms	Subjects will respond to a verbal open-ended symptoms questionnaire
6.6	Subjective Acceptance	Record whether the subject's distance and near vision with the lenses is acceptable.
6.7	Distance and Near Entrance Visual Acuity	
Distance and near Snellen visual acuity will be measured for each eye with the study contact lenses in place.
 
For near measures use the ETDRS 2000 Series Chart 1 or 2.
 
The acuity will be recorded to the nearest letter OD, OS and OU.

6.8	Visual Performance Distance (4M) Intermediate (64 cm) Near (40 cm)	
Visual performance will be recorded OD, OS, and OU for the following:
 
Distance, Bright Illuminance High and Low Contrast ETDRS Charts 4M- HC#1, HC#2, HC#3 and LC#1, LC#2,

Clinical Study Protocol
Johnson & Johnson Vision Care, Inc.

		
LC#3
 
Near, Bright Illuminance
 
Reduced Guillon-Poling Charts
 
Intermediate (64 cm) High Contrast and Low Contrast
 
Near (40 cm) High Contrast and Low Contrast
 
Distance, Dim Illuminance (with Distance goggles)
 
High Contrast ETDRS Charts
 
4M-HC#4, HC#5, HC#6
 
Near, Dim Illuminance (with Near goggles)
 
Reduced Guillon-Poling charts
 
High Contrast Intermediate (64 cm) and Near (40 cm).
 
Note:
 
 • The room illuminance must be between 7.3 and 7.9 EV (394-597 lux). • Distance, HC-1 Chart luminance Acceptable Range 10.5-10.7 EV (181-208 cd/m²). • Guillon-Poling, Near Chart Luminance Acceptable Range 10.8-11.1 EV (223-274 cd/m²). • Do not use the Mesopic filter for Dim luminance (Dim luminance will be simulated by using the goggles) 	
6.9	Binocular Distance Over-refraction and Distance Visual Acuity	
Perform a binocular over-refraction and record the OD and OS results and distance visual acuity.
 
Note: No lens changes are allowed based on the over-refraction.
	Appendix D

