6.10	Lens Fit Assessment	
Evaluate and grade lens centration, primary gaze movement, upgaze movement and tightness (push-up test).
 
The subject should not proceed to wear the lenses if any of the following is observed:
 
 • presence of limbal exposure (appearance of clear cornea) in any gaze • presence of edge lift • presence of unacceptable movement (excessive or insufficient) in all three 	

Clinical Study Protocol
Johnson & Johnson Vision Care, Inc.

		
movement categories (primary gaze, upgaze, and push-up).
 
If either lens is deemed unacceptable, the subject will be discontinued from the study. Remove the lenses, perform a slit-lamp evaluation, and complete the Final Evaluation form.
	
6.11	Lens Deposits	Grade and record the amount of front and back surface lens deposits for both eyes.	[REDACTED]
6.12	Lens Wettability	Grade the wettability of the lens.	[REDACTED]
6.13	Collection of unworn lenses (if applicable)	Collect unworn lenses returned by the subject.	
6.14	Lens Removal	
Have the subject remove the study lenses and store in saline in a labeled glass vial.
 
Note: The lenses do not need to be stored in a refrigerator.
	
6.15	Biomicroscopy	
Perform Biomicroscopy OD and OS. Slit Lamp Classification Scales will be used to grade the findings.
 
For the conjunctival redness [REDACTED] 0.5 unit increments will be used in the grading.
 
Corneal Staining Assessment [REDACTED] will be graded in 1.0 increments.
 
If any of these slit lamp findings are Grade 3 or higher, an AE must be recorded. All AEs must be followed to resolution.
 
If the clearance of the fluorescein needs to be expedited, preservative-free rewetting drops may be instilled.
	[REDACTED]

FINAL EVALUATION

The final evaluation will ordinarily take place immediately following the last scheduled follow-up visit per the study protocol. It may also take place at any point the subject discontinues the study or is terminated from the study.

Clinical Study Protocol
Johnson & Johnson Vision Care, Inc.

Final Evaluation		
Step	Procedure	Details
F.1	Distance Subjective Sphero-cylindrical Refraction and Distance Exit Visual Acuity	Perform bare-eye subjective spherocylindrical refraction with a phoropter and record the best corrected distance visual acuity to the nearest letter (OD, OS, and OU). [REDACTED]

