F.2	Subject Disposition	Indicate if the subject completed the study successfully. If subject discontinued from the study indicate the reason. [REDACTED]

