8. SUBJECTS COMPLETION/WITHDRAWAL

8.1. Completion Criteria

Subjects are considered to have completed the study if they:

- provided informed consent
- they are eligible
- completed all study visits

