8.2. Withdrawal/Discontinuation from the Study

A subject will be withdrawn from the study for any of the following reasons:

- Subject death during the study period
- Subject withdrawal of consent
- Subject not compliant to protocol
- Subject lost to follow-up
- Subject no longer meets eligibility criteria (e.g. the subject becomes pregnant)
- Subject develops significant or serious adverse events causing discontinuation of study lens wear
- Subjects who have experienced a Corneal Infiltrative Event (CIE)
- Investigator's clinical judgment regarding the subject safety reasons (that it is in the best interest of the subject to stop treatment)
- Subject missed two consecutive study visits
- Subject not compliant with study lens wear schedule
- Subject not successfully dispensed due to lack of efficacy and safety including poor vision, poor comfort or unacceptable fit

For discontinued subjects, the Investigator will:

- Complete the current visit (scheduled or unscheduled)
- Complete the Final Evaluation, indicating the reason that the subject was discontinued from the study

Clinical Study Protocol

Johnson & Johnson Vision Care, Inc.

- Record the spherocylindrical refraction with best corrected distance visual acuity
- Collect used test article(s) (worn or brought to the visit) from the subject and discard them, unless otherwise stated in Section 7.2
- Collect all unused test article(s) from the subject

An additional subject may be enrolled if a subject discontinues from the study prematurely.

In cases where a subject is lost to follow-up, every possible effort must be made to contact the subject and determine the reason for discontinuation/withdrawal. The measures taken to follow up must be documented including two written attempts and a certified letter (or equivalent) as the final attempt.

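### Step 3.10 discontinues a subject for poor fit of a lens whose wear is already over, which cancels period 2; step 6.10 repeats the rule and leaves the final disposition inconsistent

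*Combined protocol and SAP*

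**What the plan says.** Section 7.2 repeats one lens-fit rule through the visits. If limbal exposure, edge lift or unacceptable movement in all three categories is seen, the subject is not to go on wearing the lenses, and "If either lens is deemed unacceptable, the subject will be discontinued from the study". The sentence stands at 1.27, 2.10, 4.14 and 5.10, and again at the period-end visits, 3.10 and 6.10. Step 4.14 words its criteria a little differently: "Evaluate overall lens fit acceptance (acceptable or unacceptable) based on centration, movement and other fitting characteristics".

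At Visits 3 and 6 the primary measurement comes first (3.8, 6.8): "Visual performance will be recorded OD, OS, and OU for the following". After the fit check every subject has the lens taken out (3.14, 6.14): "Have the subject remove the study lenses and store in saline in a labeled glass vial". Visit 3 ends with step 3.17: "The subject will complete a wash-out period and be scheduled to return for their next visit".

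Section 8.1 defines completion by consent, eligibility and having "completed all study visits", with no fit condition. Section 8.2 names unacceptable fit only as a reason for not being successfully dispensed, and has the investigator finish the visit under way for a discontinued subject. Step F.2 reads: "Indicate if the subject completed the study successfully. If subject discontinued from the study indicate the reason". Section 14.3 limits the per-protocol set to successful completers without substantial deviations. Sections 14.3 and 14.5 make that set primary and the ITT population the sensitivity analysis.

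**The concern.** A rule that stops further wear is useful only where wear follows. At 3.10 the first lens has done its work: its primary acuities are recorded and it is about to be removed for good. What the rule stops is the second lens, which the subject has not yet tried. In a 2×2 crossover this costs the subject's within-subject contrast. The trigger is a lens-related grade given after randomization, and Section 5.2 says the site staff who collect the data know which lens is being worn. In a non-inferiority trial with a per-protocol primary set, such exclusions are best kept to those that serve a purpose.

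At 6.10 the data from both periods are already in hand. The only question is which disposition is recorded and whether that label could affect per-protocol membership.

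**Working it through.** **1. Where the rule has something to stop**

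| Step | Wear of the graded lens still to come | What a failed fit changes |
|---|---|---|
| 1.27, 4.14 | 2 to 4 days | Lens not dispensed |
| 2.10, 5.10 | 10 to 14 days | Lens not dispensed |
| 3.10 | None (acuities at 3.8, removal at 3.14) | Visits 4 to 6 cancelled |
| 6.10 | None (acuities at 6.8, removal at 6.14) | Disposition label only |

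Only deposits, wettability and collection of unworn lenses come between the fit check and removal (3.11 to 3.13, 6.11 to 6.13). Nothing in the documents exempts Visits 3 or 6.

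**2. Consequence at 3.10.** Discontinued at 3.10, so no Visits 4 to 6, so 8.1 is not met, so not in the per-protocol set (14.3), so absent from the primary analysis (14.5). The ITT set keeps the subject. The repeated-measures model in 14.5, with unstructured within-subject covariance, can use the period 1 acuity without imputation. The subject's own Test-minus-Control difference is still never observed. Section 14.9 imputes nothing by default and leaves multiple imputation optional.

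**3. Consequence at 6.10.** A failed fit there calls for lens removal, slit-lamp examination and Final Evaluation, which every subject has anyway (6.14, 6.15, F.1 and F.2). With Visit 6 finished as 8.2 directs, a subject who otherwise satisfies 8.1 is a completer under 8.1 and discontinued under 6.10. No text says which status F.2 should carry, or which one the per-protocol definition reads.

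**4. Does misfit of the first lens predict misfit of the second?** Section 1.1 gives both lenses the same diameter and aspheric back surface design. Table 1 gives 14.3 mm for both, nominal base curves of 8.35 and 8.4 mm, and different materials (senofilcon A, 38% water; etafilcon A, 58% water). Misfit of one may be informative about the other without settling it. Steps 4.14 and 5.10 check the second lens directly.

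**5. Size.** The plan's own figures come first. For near vision, high luminance low contrast, Table 5 gives SDs of 0.103 and 0.130, ICC 0.69 and n = 40. The SD of the difference is √(0.103² + 0.130² − 2 × 0.69 × 0.103 × 0.130) = 0.0950. A paired t-test with margin 0.05, true difference 0, one-sided 2.5% and 90% power gives n = 40 (power 90.1%). All nine rows reproduce: 31, 29, 31, 34, 38, 36, 36, 40, 40.

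The documents give no fit-failure rate, so I assume 1% to 4% per visit, on top of the planned 7% loss (Section 14.2):

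- Completers before any fit loss: 48 × 0.93 = 44.64.
- Lost at 3.10: 48 × 0.01 = 0.48 to 48 × 0.04 = 1.92.
- Remaining: 44.64 − 0.48 = 44.16 to 44.64 − 1.92 = 42.72.
- If every Visit 6 case were excluded as well: 44.16 × 0.99 = 43.72 to 42.72 × 0.96 = 41.01.

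All stay above 40. Losses at 3.10 alone would reach the target only at a rate of 4.64 / 48 = 9.7%. One completer below 40 would put power at 89.3% on this endpoint.

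**The case against.** The strongest defense is caution at 3.10. The two lenses share diameter and back surface design, so limbal exposure or edge lift with one could foretell the same with the other, and stopping spares the subject a fitting that may fail. That stands in part: the misfit may be informative, and whether to stop or refit is partly a design preference. But the plan does not give this reason, and safeguards already exist: slit-lamp examination at 3.15 and 4.5, the continuance decision at 4.6, the second lens's own check at 4.14 before it is dispensed, and investigator safety judgment in 8.2.

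It can also be said that 6.10 changes almost nothing. That is right. Sections 8.1 and 8.2 together already favor completer status, a fit grade is an outcome and not a protocol deviation, a cohort review committee judges deviations before database lock with exclusions documented, and the ITT analysis keeps the pair.

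A reader might infer three stronger points that the documents do not support:

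- *That 6.10 requires a complete pair to be dropped from the primary analysis.* Exclusion is possible, because the label is ambiguous, but nothing prescribes it.
- *That the lack of imputation removes a 3.10 subject from the ITT analysis.* The planned model can use the period 1 observation.
- *That the rule tilts the comparison toward Test.* The documents link fit failure neither to one lens nor to acuity, so neither the direction nor the size of any bias can be derived.

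**Conclusion.** The point holds, mainly for step 3.10. A rule written to protect wear that is about to start is applied where that wear is over. Its effect there is to lose period 2 and per-protocol membership. Step 6.10 is secondary: an inconsistent disposition that could, but need not, lead to a per-protocol exclusion.

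The expected effect is small. The triggers are specific signs, and the fit has already passed the same check at the optimization visit. The head-count range rests on an assumed 1% to 4% failure rate per visit; within it, power is not at stake. The reading of the text is firm, but the practical consequence depends on a rate the documents do not give. This is a cheap improvement and does not threaten the trial's conclusions.

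**What to change.** - **3.10 and 6.10:** delete the bar on further wear and the discontinuation sentence. Keep the fit grading, which Section 2.2 already lists among the other endpoints.
- **3.10, add:** *Record the grade, remove the lens (3.14) and continue to Visit 4 unless 8.2 requires withdrawal; the second lens is checked at 4.14.*
- **F.2, add:** *A Visit 6 fit grade does not by itself prevent completion under 8.1.* This leaves the eligibility and all-visits conditions of 8.1 intact.
- **14.3, add:** *A Visit 3 or Visit 6 fit grade alone is not a reason for exclusion from the per-protocol population.*

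The cost is deletions at two steps and three added sentences, with no new assessment. The downside is that a subject with a poor first-lens fit attends Visit 4 and may then fail the second-lens check. Investigator safety judgment under 8.2 stays in force throughout.

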7.3. Unscheduled Visits

If, during the investigation, a subject requires an unscheduled visit to the clinical site, the following information will be collected at a minimum:

- Chief complaint prompting the visit. If the reason is an adverse event, the applicable eCRF for the adverse event must be completed and subject record completed as appropriate.
- Date and time of the visit and all procedures completed at the unscheduled visit.
- Review of adverse event and concomitant medications.
- Documentation of any test article dispensed or collected from the subject, if applicable.
- Slit lamp findings (using the Slit Lamp Classification Scale).

If the Investigator withdraws a subject from the study, the final study visit case report forms must be completed indicating the reason(s) why the subject was withdrawn. The subject record must be completed documenting the date and primary reason for withdrawal and the study CRA notified.

Any ocular and non-ocular Adverse Events that are ongoing at the time of the study visit will be followed by the Investigator, within licensure, until they have resolved, returned to pre-treatment status, stabilized, or been satisfactorily explained. If further treatment i.e., beyond licensure is required, the subject will be referred to the appropriate health care provider.

The following information will be collected during an unscheduled visit.

Unscheduled Visit		
Step	Procedure	Details
U.1	Chief Complaints	Record the subject's chief complaints for reasons for the unscheduled visit [REDACTED]
U.2	Adverse Events and Concomitant Medications Review	Review the subject's concomitant medications and record any changes from the previous study visit. [REDACTED]
U.3	Subject Reported Ocular Symptoms	Subjects will respond to a verbal open-ended symptoms questionnaire. [REDACTED]
U.4	Entrance VA	Record the entrance distance and near visual acuity (OD, OS and OU). [REDACTED]

Clinical Study Protocol
Johnson & Johnson Vision Care, Inc.

Unscheduled Visit			
		
For near measures use the ETDRS 2000 Series Chart 1 or 2.
 
The acuity will be recorded to the nearest letter OD, OS and OU.
	
U.5	Subjective Sphero-cylindrical Refraction	
An optimal, binocular balanced distance sphero-cylindrical refraction will be performed.
 
Record the refraction and distance visual acuity to the nearest letter.
	
U.6	Biomicroscopy	
FDA Slit Lamp Classification Scale will be used to grade the findings..
 
For the conjunctival redness [REDACTED] 0.5 unit increments will be used in the grading.
 
Corneal Staining Assessment [REDACTED] will be graded in 1.0 increments.
 
If any of these slit lamp findings are Grade 3 or higher, an AE must be recorded. All AEs must be followed to resolution.
 
If the clearance of the fluorescein needs to be expedited, preservative-free rewetting drops may be instilled.
	
U.7	Lens Dispensing	
Additional study lenses may be dispensed when required.
	
U.8	Lens Fit Assessment:	
Evaluate and grade lens centration, primary gaze movement, upgaze movement and tightness (push-up test).
 
The subject should not proceed to wear the lenses if any of the following is observed:
 
 • presence of limbal exposure (appearance of clear cornea) in any gaze • presence of edge lift • presence of unacceptable movement (excessive or insufficient) in all three movement categories (primary gaze, upgaze, and push-up). 
If either lens is deemed unacceptable, the subject will be discontinued from the study. Remove the lenses, perform a slit-lamp
	

Clinical Study Protocol

Johnson & Johnson Vision Care, Inc.

Unscheduled Visit			
		evaluation, and complete the Final Evaluation form.	
U.9	Exit Visual Acuity	Record the subject's exit distance and near visual acuity (OD, OS and OU). For near measures use the ETDRS 2000 Series Chart 1 or 2. The acuity will be recorded to the nearest letter OD, OS and OU.	[REDACTED]

7.4. Laboratory Procedures

Not Applicable

8. SUBJECTS COMPLETION/WITHDRAWAL

8.1. Completion Criteria

Subjects are considered to have completed the study if they:

- provided informed consent
- they are eligible
- completed all study visits

